## Data Sharing

N/A

## Sample Size Determination

Sample size was calculated based on our pilot study showing that the incidence of death or BPD among extremely preterm infants with early pulmonary hypertension was 80%. Assuming a 30% relative decrease of the incidence we came up with a sample size of 34 infants in each arm with 80% power and alpha of 0.05.

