### Study Site(s)/Location(s) and Number of Subjects

This is a single site clinical study to be conducted at the Neonatal Intensive Care Unit of AdventHealth for Children. A total of 136 infants will be enrolled in the trial, and 68 of those infants will be randomized (34 in each arm). Screen failures, which are defined as infants who were consented but the echocardiogram showed no PH, will be enrolled into the comparison group and no further intervention will occur for them. To compare the incidence of death or BPD, outcome data will continue to be collected on the comparison group for the duration of their hospital stay.

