## Statistical Analysis Plan

### Primary Objective Analysis

Data will be analyzed to define the demographic and clinical characteristics of the two study cohorts (iNO and placebo) and the infants without early PH (not enrolled for treatment, please see Fig. 1). Chi square test for categorical variables and student's t test or non-parametric equivalent test for continuous variables will be used. Relative Risk (with 95% CI) for death or BPD will be calculated for the placebo and iNO treatment groups. The outcomes of infants without early PH will also be compared with the two study cohorts (iNO and placebo). Logistic regression will be performed to adjust for significant covariates if needed (unlikely because of randomization and stratification). Similarly, treatment and placebo groups will be compared to determine the short-term benefits of iNO treatment for PH in preterm infants.

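### 34 infants per arm gives about 57% power, not 80%, for the stated 30% relative reduction from 80%

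*Combined protocol and SAP*

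**What the plan says.** The combined protocol and SAP justifies the trial's size in one short paragraph, under Sample Size Determination. The control rate is from a pilot study in which "the incidence of death or BPD among extremely preterm infants with early pulmonary hypertension was 80" per cent. The effect and the resulting size are then given together: "Assuming a 30% relative decrease of the incidence we came up with a sample size of 34 infants in each arm with 80% power", at an alpha of 0.05. The section on study sites and number of subjects repeats the figure: "68 of those infants will be randomized (34 in each arm").

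The sample-size paragraph does not state sidedness, the test or formula used, or any allowance for losses. The Primary Objective Analysis section names a "Chi square test for categorical variables" and adds: "Relative Risk (with 95% CI) for death or BPD will be calculated for the placebo and iNO treatment groups". No other section gives a different effect size or power.

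**The concern.** The paragraph gives all the main inputs, so the calculation can be repeated, and it does not come out at 34. The gap is too large to be rounding or a choice of formula.

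This paragraph is the only justification for the trial's size on its primary endpoint, death or BPD at 36 weeks postmenstrual age. The IRB, the funder and the monitoring board would all take the 80% at face value. If iNO has exactly the assumed effect, the chance of missing it is about double what the plan states. A non-significant result set beside a claimed 80% power invites the conclusion that a 30% reduction has been ruled out, and this design could not support that.

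**Working it through.** **Inputs**

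- Control rate p1 = 0.80, effect 30% relative, n = 34 per arm, power 0.80, alpha 0.05: Sample Size Determination.
- Treated rate p2 = 0.80 × (1 − 0.30) = 0.56, a difference of 0.24.
- Allocation 1:1, 68 randomized: section on study sites and number of subjects.
- Two-sided test: an assumption, in line with the planned chi-square test and 95% confidence interval. One-sided results are also shown.

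**Attempt to reproduce 34 per arm**

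The pooled two-proportion formula, with p̄ = (0.80 + 0.56)/2 = 0.68, is

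n = [z(α/2)·√(2p̄(1−p̄)) + z(β)·√(p1(1−p1) + p2(1−p2))]² / (p1−p2)²

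- First term: 1.960 × √(2 × 0.68 × 0.32) = 1.960 × 0.6597 = 1.293
- Second term: 0.842 × √(0.16 + 0.2464) = 0.842 × 0.6375 = 0.537
- n = (1.293 + 0.537)² / 0.24² = 3.347 / 0.0576 = 58.1, so 59 per arm

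The stated 34 is not reproduced. Other methods on the same inputs do not reach it either:

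| Method | n per arm, two-sided 0.05 | n per arm, one-sided 0.05 |
|---|---|---|
| Pooled | 59 | 46 |
| Unpooled | 56 | 44 |
| Arcsine | 58 | 46 |
| Log relative risk | 64 | 51 |
| Continuity-corrected | 67 | 54 |

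**Power at 34 per arm**

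Power = Φ{[0.24 × √34 − 1.293] / 0.6375} = Φ{(1.399 − 1.293)/0.6375} = Φ(0.167) = 56.6%

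| Method | Two-sided | One-sided |
|---|---|---|
| Pooled normal | 56.6% | 68.9% |
| Unpooled normal | 59.3% | 70.9% |
| Arcsine | 57.8% | 69.6% |
| Log relative risk | 53.3% | 65.5% |
| Exact, uncorrected chi-square | 58.9% | 70.0% |
| Exact, Fisher | 47.6% | 59.2% |

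**Shortfall**

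The plan has 68 infants where 118 are needed: (118 − 68)/118 = 42% short.

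**What 34 per arm does support**

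Solving the pooled formula for p2 at 80% power gives p2 = 0.479, a relative reduction of 1 − 0.479/0.80 = 40%. At exactly 80% versus 48%, n = 34.1 (35 after rounding up) and power at 34 is 79.9%. The documents do not say that this effect was used, so it describes what 34 can detect and does not explain where the number came from.

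**Further erosion (assumed rates; the documents give none)**

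- The plan excludes withdrawn infants from the final analysis. With an assumed 10% loss (34 × 0.9 = 30.6 per arm), pooled power falls to about 52%.
- The plan lets placebo infants receive iNO in some circumstances and applies intention to treat to those who are unmasked. Suppose 10% to 20% of placebo infants receive it and gain its full effect. The placebo rate becomes 0.80 − 0.10 × 0.24 = 0.776, or 0.80 − 0.20 × 0.24 = 0.752. Pooled normal power falls from 57% to 47% and 38%. Exact chi-square power falls from 59% to 49% and 40%.

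**The case against.** The best defence is that the 30% was meant as 30 percentage points (80% versus 50%) with a one-sided test. That needs 31 per arm by the pooled formula, and 34 per arm then has 84% power, so 34 would be enough. But the paragraph calls the decrease relative, nothing in the plan indicates one-sided testing, and the primary analysis reports a 95% confidence interval. Two-sided, even the 30-point reading needs 39 per arm pooled (36 unpooled). The reading therefore changes two inputs and still does not give 34. What it does show is that the failure belongs to the effect as stated; 34 could be adequate for some other, larger effect.

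A second objection is that one figure of 57% depends on the method. It does: two-sided power runs from 48% (Fisher) to 59%. Naming the test settles which value applies, and no value is near 80%.

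A third is that a single site may not be able to recruit more infants. That could justify 34 per arm, but not describing the power as 80%.

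The erosion figures rest on assumed rates and are illustrative. The main result does not depend on them.

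**Conclusion.** The error is real and needs correcting. For 80% versus 56% at two-sided 0.05, 34 per arm gives about 57% power (48% to 59% across methods), against the stated 80%. The stated power needs about 59 per arm, or 56 to 67 depending on the formula. The result rests on the plan's own control rate, relative effect, alpha and arm size. The one assumption is two-sidedness, and the conclusion survives without it: one-sided power is about 69% pooled and at most 71%. The detectable effect at 80% power is a relative reduction of about 40%, a third larger than the plan assumes (40/30 = 1.33). How 34 was obtained cannot be told from the documents.

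**What to change.** Rewrite the sample-size paragraph, leaving enrolment as it is:

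- State the two rates (80% and 56%), the sidedness and the test.
- State that 34 per arm gives about 57% power for this effect (two-sided 0.05, normal approximation to the chi-square test), and 80% power only for a relative reduction of about 40% (80% to 48%). If a continuity-corrected or Fisher test will be used, give that figure instead (about 48% for 80% versus 56%).
- State that there is no allowance for withdrawals or for iNO given to placebo infants, so power may be lower.
- State that a non-significant result will be interpreted through the 95% confidence interval for the relative risk, which is already planned, and not as showing that a 30% reduction is absent.

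This costs a wording amendment and a less favourable power statement. It adds no infants.

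If the sponsor would rather keep 80% power for a 30% reduction, the alternative is about 59 per arm before losses (67 with continuity correction). At the plan's own ratio of two enrolled for each one randomized (136/68), 118 randomized means about 236 enrolled, against the 362 infants the plan expects to be available over three years before consent. Whether that is feasible is for the sponsor to decide. Under either option the present sentence has to change.

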## Statistical Analysis Plan

### Primary Objective Analysis

Data will be analyzed to define the demographic and clinical characteristics of the two study cohorts (iNO and placebo) and the infants without early PH (not enrolled for treatment, please see Fig. 1). Chi square test for categorical variables and student's t test or non-parametric equivalent test for continuous variables will be used. Relative Risk (with 95% CI) for death or BPD will be calculated for the placebo and iNO treatment groups. The outcomes of infants without early PH will also be compared with the two study cohorts (iNO and placebo). Logistic regression will be performed to adjust for significant covariates if needed (unlikely because of randomization and stratification). Similarly, treatment and placebo groups will be compared to determine the short-term benefits of iNO treatment for PH in preterm infants.

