## Randomization

Randomization into 2 groups will be done using statistical software (SAS or Excel). To keep the balance between treatment and placebo groups, we will use stratified permuted block randomization. Randomization will be stratified by gestational age (230/7-256/7 weeks, 260/1-296/7 weeks) and severity of PH (moderate & severe). Because the number of enrolled infants per stratification group is unknown at the start of the study, additional envelopes will be generated with randomization sequences of various block sizes balanced between placebo and treatment. The envelopes will remain sealed until the infant has been enrolled in the study. The envelopes will be kept in a secured office in the RT department that will be accessible to only trained, unblinded RT personnel. Documents regarding the randomization process will be kept in the RT department. The randomization envelope will be pulled by one of the trained, unblinded RT personnel who will obtain the corresponding treatment/placebo tank prior to the initiation of intervention.

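### Adjustment is optional and unspecified when the non-randomised no-PH infants are compared with the two arms, and the reason given for not expecting it holds only for iNO versus placebo

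*Combined protocol and SAP*

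**What the plan says.** **How the group is formed.** Under Study Site(s)/Location(s) and Number of Subjects: "A total of 136 infants will be enrolled in the trial, and 68 of those infants will be randomized (34 in each arm". The rest come from screening: "Screen failures, which are defined as infants who were consented but the echocardiogram showed no PH, will be enrolled into the comparison group". Their follow-up has a stated purpose: "To compare the incidence of death or BPD, outcome data will continue to be collected on the comparison group". Death or BPD is the trial's primary endpoint.

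**How it is analysed.** The Primary Objective Analysis section first describes the characteristics of all three groups and names the tests: "Chi square test for categorical variables and student's t test or non-parametric equivalent test for continuous variables will be used". It then names the effect measure for the randomised arms: "Relative Risk (with 95% CI) for death or BPD will be calculated for the placebo and iNO treatment groups". The no-PH comparison follows: "The outcomes of infants without early PH will also be compared with the two study cohorts (iNO and placebo". The next sentence is the only one on adjustment: "Logistic regression will be performed to adjust for significant covariates if needed (unlikely because of randomization and stratification".

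**What randomisation covers.** Under Randomization: "Randomization will be stratified by gestational age", and also by PH severity. Only infants found to have PH are randomised.

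**What is collected.** The Data Collection section lists gestation and birth weight for the neonates.

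**The concern.** The sentence on adjustment directly follows the sentence on the no-PH comparison, and the reason it gives cannot apply there. Randomisation and its strata balance iNO against placebo. They do nothing to balance either arm against infants sorted by an echocardiogram finding.

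Eligible infants span 23 to 29 completed weeks and may be on a ventilator or on CPAP, so maturity and illness can differ widely between those with and without PH. The plan stratifies on gestational age, which suggests that its authors regard it as prognostic. If gestational age differs by PH status, a crude gap between placebo and no-PH infants mixes the effect of PH with the effect of immaturity. Likewise, a crude similarity or gap between iNO and no-PH infants says little about the treatment.

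What is at stake is how this reference comparison is interpreted, not the trial's primary test.

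**Working it through.** **1. Does the stated reason reach the no-PH group?**

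| Comparison | Formed by randomisation? | Gestational-age strata apply? | Reason for not adjusting holds? |
|---|---|---|---|
| iNO vs placebo | Yes | Yes | Yes |
| Placebo vs no-PH | No, by echocardiogram | No | No |
| iNO vs no-PH | No, by echocardiogram | No | No |

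The no-PH group is about 136 − 68 = 68 infants, so each comparison with an arm is about 34 against 68.

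**2. How large could the bias be?** The plan gives no figure for this comparison, so there is none to reproduce. It gives neither the gestational-age mix by PH status nor death/BPD rates by gestational age. All inputs below except the group sizes are therefore assumptions.

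Take two gestational-age groups, with the same risk for PH and no-PH infants within each group (no true PH effect). Let q be the share of infants in the lower group.

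- Crude risk = q × risk(low) + (1 − q) × risk(high)
- Spurious difference = (q in PH − q in no-PH) × (risk(low) − risk(high))

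Worked example: shares 70% and 30%, risks 80% and 40%.

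- PH: 0.70 × 0.80 + 0.30 × 0.40 = 0.68
- No PH: 0.30 × 0.80 + 0.70 × 0.40 = 0.52
- Difference 0.16; RR 0.68/0.52 = 1.31

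The last column is the probability that an unadjusted two-sided 5% chi-square test of 34 placebo versus 68 no-PH infants is significant, by exact enumeration.

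| Low-GA share, PH / no-PH | Risk low / high GA | Crude risk, PH / no-PH | Difference (points) | RR | Rejection |
|---|---|---|---|---|---|
| 60% / 60% | 90% / 60% | 78% / 78% | 0 | 1.00 | 5% |
| 50% / 40% | 70% / 50% | 60% / 58% | 2 | 1.03 | 6% |
| 60% / 40% | 90% / 60% | 78% / 72% | 6 | 1.08 | 9% |
| 60% / 40% | 80% / 40% | 64% / 56% | 8 | 1.14 | 13% |
| 70% / 30% | 90% / 60% | 81% / 69% | 12 | 1.17 | 25% |
| 70% / 30% | 80% / 40% | 68% / 52% | 16 | 1.31 | 36% |

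The 90%/60% rows lie closest to the one relevant figure in the documents, the 80% death or BPD with early PH under Sample Size Determination. With unequal mixes they give 6 and 12 points. If PH infants were the more mature group, the sign would reverse.

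**3. Would the optional regression catch an imbalance?** The plan does not say what makes a covariate significant. Suppose it means a significant difference between groups at the two-sided 5% level. With low-GA shares of 60% of 34 and 40% of 68, exact enumeration gives a 51% chance that the chi-square test flags the difference. With 70% and 30%, the chance is 98%. The rule would usually catch an extreme imbalance, but would miss a moderate one about half the time.

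**The case against.** The strongest reply has four parts.

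- **Adjustment is not ruled out.** A reader might infer that the no-PH comparison will be made with no adjustment at all. The documents do not say that. The logistic regression sentence is not restricted to iNO versus placebo, and the section begins by describing all three groups, so a difference in gestational age would be seen. The named tests follow the sentence on characteristics, and no test is tied specifically to the no-PH outcome comparison. This part stands. What remains is that adjustment is optional, driven by significance and without named covariates.
- **Confounding is not shown.** A reader might also infer that gestational age does confound the comparison. The documents give no gestational-age distribution by PH status. All screened infants must be on positive pressure support at 48-96 hours, which narrows the difference in illness without removing it. This part stands too: confounding is plausible, not demonstrated.
- **No claim rests on this group.** Neither study objective involves the no-PH infants, the screening section calls them a reference group, and the relative risk is named only for the randomised arms. A reader might fear a claim that iNO restores normal risk, but none is planned. This limits the consequence. It does not settle how the planned comparison should be done.
- **The size is assumed.** True, and equal mixes give no bias at all.

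None of these replies rescues the stated reason for not expecting adjustment, which does not apply to a group formed by echocardiogram.

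**Conclusion.** The concern holds as a minor point. The plan compares death or BPD between about 68 non-randomised infants and each arm. It leaves adjustment optional and unspecified, and it gives a reason for not expecting adjustment that is valid only for iNO versus placebo. The comparison is open to confounding by gestational age and illness severity.

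The size cannot be derived from the documents. On the assumed two-group inputs with no true PH effect, it runs from 0 points with equal gestational-age mix to 16 points with a 70% versus 30% mix, and rejection runs from about 5% to 36%. These figures cover gestational age only and assume that PH infants are the less mature group. The randomised comparison of iNO with placebo is unaffected.

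**What to change.** In the Primary Objective Analysis section:

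1. Limit the remark about randomisation and stratification to iNO versus placebo.
2. For death or BPD in no-PH infants versus each arm, pre-specify a logistic or modified Poisson model that includes gestational age regardless of significance. Name any further baseline covariates in advance and keep them few. In the 70%/30% row with risks of 90%/60%, for example, only about 34 × 0.19 + 68 × 0.31 = 28 infants would be free of the outcome.
3. Report the result as a non-randomised, observational association.

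Baseline-characteristic comparisons need no adjustment.

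The cost is a change of wording and one more model, on data already collected. Intervals will be somewhat wider than for the crude comparison, and adjusting for gestational age will not remove confounding by unmeasured illness severity.

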### **Data Collection:**

Demographic and clinical data will be prospectively collected from maternal and neonatal charts along with data from serial echocardiograms. Following variables will be included in the database

- **Maternal Data:** Age, ethnicity, educational level, smoking, alcohol or illicit use of drugs, medication history, any medical or surgical problem, antenatal screening lab results (GBS, HIV, HBs Ag, RPR) maternal UTI, chorioamnionitis, rupture of membrane, vaginal bleeding or discharge, antenatal antibiotics, steroids, indomethacin or magnesium.
- **Neonatal Data: BPD our primary outcome is determined based on the need for positive pressure ventilation or supplemental oxygen after room air challenge test**  
Gestation, Gender, mode of delivery, Apgar scores, IUGR, Birth Weight, Surfactant, Ventilation, pulmonary hypertension (early, intermittent or late), use of supplemental oxygen, culture proven infections, blood transfusions, Cardiotropic medication, bicarb infusion, saline boluses, use of indomethacin, PDA treatment/ ligation, use of diuretics, use of postnatal steroids, IVH, PVL, Post IVH hydrocephalus, NEC, ROP, ROP requiring treatment, VP shunt, Tracheostomy, Gastrostomy tube, home oxygen, home ventilation, length of hospital stay and death.

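### Randomisation is stratified by gestational age and PH severity, but the plan commits to no analysis that uses either factor and leaves adjustment to unnamed covariates

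*Combined protocol and SAP*

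**What the plan says.** Under Randomization: "Randomization will be stratified by gestational age" (two groups) and by PH severity (moderate or severe), in permuted blocks. That makes four strata for 68 infants. The same section concedes that their sizes are not known: "Because the number of enrolled infants per stratification group is unknown at the start of the study".

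Under Primary Objective Analysis, the tests are listed generally, beginning "Chi square test for categorical variables". For the primary outcome: "Relative Risk (with 95% CI) for death or BPD will be calculated for the placebo and iNO treatment groups". The only mention of adjustment is: "Logistic regression will be performed to adjust for significant covariates if needed (unlikely because of randomization and stratification".

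Secondary Objective Analysis names no model and no stratification factor. Data Collection lists many candidate covariates, maternal ("Age, ethnicity, educational level, smoking, alcohol or illicit use of drugs, medication history") and neonatal ("Gestation, Gender, mode of delivery, Apgar scores, IUGR, Birth Weight, Surfactant").

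**The concern.** There are two gaps.

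First, the SAP cites stratification as a reason not to adjust. The usual reasoning is the reverse. Stratified allocation forces balance on factors thought to be prognostic, so the treatment difference varies less from trial to trial than a crude standard error assumes. If the analysis ignores the strata, the reported interval is wider than it should be and the test rejects less often than 5% under the null.

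Second, the adjustment clause fixes nothing. *Significant* could mean different between arms or associated with outcome. *Needed* has no trigger, and no covariate is listed. Several analyses of the primary outcome therefore remain open, on two effect scales, and nothing prevents the choice from being made once results are known. In a single-site trial of 68 infants, the result could depend on that choice.

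**Working it through.** **Inputs from the documents.** 34 per arm; 80% death or BPD without treatment; "Assuming a 30% relative decrease of the incidence", so the treated risk is 0.80 × 0.70 = 0.56; alpha 0.05. Sidedness is not stated; two-sided is assumed.

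**The plan's own figure.** n = [1.96√(2·0.68·0.32) + 0.842√(0.80·0.20 + 0.56·0.44)]² / 0.24² = (1.293 + 0.537)² / 0.0576, which rounds up to 59 per arm, not 34. Power at 34 per arm is about 57% (normal approximation) to 59% (exact). This is a separate issue and the present point does not depend on it. It does explain why power below is near 59% rather than 80%.

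**Change of effect measure.** A relative risk of 0.70 at these rates is an odds ratio (OR) of (0.56/0.44)/(0.80/0.20) = 0.32. Expected infants without the event: 34 × 0.20 + 34 × 0.44 = 21.8, about 22, which supports very few covariates.

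**Why the crude test is conservative.** With allocation balanced within strata, the null variance of the treatment difference, relative to what the crude test assumes, is R = Σ w·p(1−p) / [p̄(1−p̄)], where w is a stratum's share and p its risk. Type I error is then about 2[1 − Φ(1.96/√R)]. The stratum risks below are assumptions, for four equal strata:

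- 88/82/80/70%: mean within-stratum variance (0.1056 + 0.1476 + 0.1600 + 0.2100)/4 = 0.1558; R = 0.1558/0.16 = 0.974; type I error about 4.7%.
- 95/90/80/55%: (0.0475 + 0.0900 + 0.1600 + 0.2475)/4 = 0.1363; R = 0.852; type I error about 3.4%.

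**Simulation.** 100,000 trials per scenario, blocks of 2 or 4, and three assumed stratum-size mixes (25/25/25/25, 10/30/15/45 and 15/50/5/30%). The stratified test is CMH without continuity correction, with the collapsing rule given in the fix. Strength is the assumed odds ratio between the extreme strata.

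| Strength (OR) | Crude type I error | CMH minus crude power, constant RR | Same, constant OR |
|---|---|---|---|
| 1 | 5.1% | −1.7 to −1.5 | −1.6 to −1.4 |
| 3 | 4.6–4.9% | −1.1 to −1.0 | −0.5 to −0.2 |
| 7 | 4.1–4.4% | −0.3 to +0.5 | +2.1 to +2.4 |
| 15 | 3.2–3.9% | +1.0 to +2.4 | +5.3 to +6.8 |
| 55 | 1.9–3.3% | +2.6 to +6.6 | +11 to +16 |

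CMH type I error is 4.8–5.0% throughout. Over the null and constant-RR scenarios, 95% interval coverage is 95.4–98.4% for the crude relative risk and 94.9–96.1% for the Mantel-Haenszel one. A separate run of 40,000 trials per scenario agreed within simulation error.

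**The open covariate clause.** 20,000 null trials per scenario, 10 or 20 independent covariates, four readings: crude; adjust for covariates that differ between arms at p<0.05; adjust for those associated with outcome; adjust for either. Any one reading fixed in advance gives 4.3–5.5%. Reporting whichever of the four is most favourable gives 5.8–6.7% with no prognostic covariate and 7.9–8.8% with three strongly prognostic ones. With an assumed pairwise correlation of 0.5 and allocation stratified on the common factor, this falls to about 5.7–6.7%.

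**The case against.** The strongest case for the plan is that its crude analysis is valid and may be the better test. The sample size assumes a relative decrease, so a constant relative risk is the plan's own model. Under it, CMH loses power at strengths 1 and 3, ties at 7 and gains only where the strata separate sharply. Strength 55 means assumed placebo risks of 98% against 47%. No stratum event rates are given, so nothing in the documents favours the scenarios in which stratifying helps. All of this stands, and it rules out selling the fix as a power gain.

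The unadjusted relative risk is also planned without condition, and logistic regression only if needed. A reader might infer that the plan carries a 6–9% type I error. It does not: that figure requires reporting the best of several analyses after seeing results, and no text says this will be done.

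A reader might also infer that chance imbalance will almost certainly trigger adjustment. With 10–20 independent covariates, at least one differs at p<0.05 in 41–66% of simulated trials (1 − 0.95^k gives 40–64%), but that is an upper range. Many of the listed variables may track gestational age, which is stratified; with correlation 0.5 the rate was about 15–27%.

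Finally, the optional logistic model does not exclude the stratification factors. It simply does not name them.

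What remains is that no analysis using the strata is committed to, and the adjustment rule is undefined.

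**Conclusion.** The point holds as a gap in specification that should be closed; it is not an error that invalidates the trial. The text is clear: two factors define the randomisation, no planned analysis is committed to either, and the adjustment clause has no covariates and no trigger.

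The size is conditional. If the strata are clearly prognostic (strength about 7 to 15), the crude test runs at about 3–4.5% type I error and its interval is too wide. If they are weak or irrelevant, the crude test loses nothing. Under a constant relative risk the difference in power runs from about 2 points against the stratified test to about 2 points or more in its favour; larger gains need a constant odds ratio, which the plan does not assume. These sizes rest on assumed stratum risks and sizes and on a two-sided test.

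Two stronger readings fail. The crude test is not anti-conservative, and stratifying would not repair the sample-size shortfall.

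**What to change.** Name one primary analysis: a two-sided CMH test without continuity correction, stratified by the four randomisation strata, with the Mantel-Haenszel relative risk and its 95% CI. Keep the crude relative risk as supportive.

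Fix one rule for sparse strata before unblinding: if any stratum has no infants in one arm, collapse to the two gestational age groups. Apply it from stratum-by-arm counts with the arms coded, without sight of outcomes by arm.

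Replace the open covariate clause with no further adjustment, or with one short sensitivity model. Its covariates should be named now and kept few, given about 22 expected non-events. Report it as a standardised relative risk, and state that it cannot replace the primary result.

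The cost is SAP wording and a few lines of code, since both factors are known at randomisation. The statistical price is about 1–2 points of power if the strata are weakly or not prognostic. If one stratum holds only 5% of infants, the collapsing rule drops PH severity in about 14% of trials, or 17% if wholly empty strata also count. Closing the covariate clause costs no power and is worth doing even if the sponsor keeps the crude test as primary.
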